6.6.1.2. Pharmacokinetic Sample Collection

Relugolix

Pharmacokinetic samples will only be collected in patients randomized to relugolix study drug.

Blood samples for pharmacokinetic analysis of relugolix will be collected at the visits indicated in the study Schedule of Activities in the protocol synopsis (see Section 1.1). The actual date and time of each blood sample collection will be recorded.

Patients may take their dose of study drug in the clinic at these visits. Study drug will be administered on an empty stomach or at least 2 hours before food, and food will be withheld for 1 hour after dosing. The date and time of their previous dose of study drug (ie, the dose the day before the clinic visit) will be accurately recorded.

Ideally, predose samples should be collected approximately 24 hours (\pm 6 hours) after the previous dose of relugolix, although samples collected outside of this window would not be considered a protocol deviation.

If the study patient inadvertently took the study drug at home on the morning of the clinic visit, the date and time of that dose should also be accurately recorded and the pharmacokinetic sample collected, which may be used for population PK modeling.

Plasma from the Week 5 and Week 13 visits in all patients will be analyzed for relugolix plasma concentration. Analysis of other individual patient plasma samples will be performed on a case-by-case basis (such as those patients with non-castrate testosterone levels).

Collection, processing, storage, and shipping instructions will be provided in the investigator site file. Plasma analysis of relugolix will be performed by the sponsor (or designee).

Leuprolide Acetate

For patients on leuprolide acetate, in the event of non-castrate testosterone levels, a blood sample may be taken for potential analysis of leuprolide acetate plasma concentration, following discussion with the medical monitor

China and Japan Pharmacokinetic Subset

In a subset of patients from China (if enrolled) and approximately 20 patients from Japan that are randomized to relugolix, additional relugolix PK samples will be collected on Day 1, Day 4, and Week 2 visits (see Schedule of Activities in the protocol synopsis, [Section 1.1](#)). The actual date and time of study drug administration and the date and time of each PK sample will be accurately recorded.

All samples from the China and Japan subset will be analyzed for plasma relugolix concentrations. Collection, processing, storage, and shipping instructions will be provided in the investigator site file. Plasma analysis of relugolix will be performed by the sponsor (or designee).

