- j. Collect serious adverse event information from the time of signed informed consent through the Safety Follow-up Visit, which is through 30 days after the last dose of relugolix or 12 weeks and 30 days after the last injection of leuprolide acetate, or the date of initiation of another investigational agent or hormonal therapy or surgical intervention, whichever occurs first. Collect nonserious adverse event information from the Baseline Day 1 visit (or from the time of signed informed consent if event was related to a screening study procedure through approximately 30 days after the last dose of relugolix or 12 weeks and 30 days after the last injection of leuprolide acetate, or the date of initiation of another investigational agent or hormonal therapy or surgical intervention, whichever occurs first).
- k. Blood samples must be obtained fasting; nothing to eat or drink (other than water) for at least 9 hours prior to obtaining the sample.
- l. All testosterone samples obtained from Week 5 and beyond are to be collected during a \pm 7-day window.
- m. Blood samples for PK analysis will be collected for all patients assigned to the relugolix treatment arm. Samples will be collected predose, approximately 24 hours after the previous dose. Patients may be dosed in the clinic at these visits, provided the dose can be administered at least 2 hours after food; food should be withheld for 1 hour after dosing.
- n. A subset of patients from China (if enrolled) and Japan will have additional samples collected predose, and 0.5, 1, 2, 4, 6, 8, 12, and 24 hours post-dose on Day 1 and Week 2 visits. Patients will be dosed in the clinic at these visits. The dose will be administered at least 2 hours after food; food should be withheld for 1 hour after dosing. A predose sample (approximately 24 hours after the previous dose) also will be collected at the Day 4 visit. Patients may be dosed in the clinic at the Day 4 visit, provided the dose can be administered at least 2 hours after food; food should be withheld for 1 hour after dosing.
- o. The blood sample for DNA should be collected at the Baseline Day 1 visit, but may be collected at any visit if it is missed at that visit.
- p. During the final weeks prior to database lock, sites will be asked to contact all study participants or their immediate family regarding the current health status of previously enrolled/completed study patients.

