- q. Week 2 visit will only occur for patients who are part of the Japan or China subset for PK analysis.
- r. For an Unscheduled visit, these procedures will be performed as needed, based on the reason(s) for the Unscheduled visit.

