In healthy, older men receiving 14 or 28 days of dosing, effective castration was consistently achieved over 14 and 28 days dosing at daily doses of 40 to 180 mg (14 days) and 80 to 160 mg (28 days). Use of a loading dose for up to 3 days (or once daily doses of ≥ 160 mg) resulted in castration levels of testosterone (< 50 ng/dL or 1.7 nmol/L) within 24 to 48 hours. Results obtained after 28 days of dosing suggested that the likely minimal, fully effective maintenance dose for sustained castration would be relugolix ≥ 80 mg once daily. Doses of 80 mg and 120 mg were moved forward into phase 2 development.

Relugolix is to be administered in the fasted state (at least 1 hour before or 2 hours after a meal), as food decreases the extent of relugolix absorption by approximately 20%. The exposure of relugolix is increased by inhibitors of P-glycoprotein up to 6-fold, but relugolix does not significantly impact the exposure of cytochrome P450 (CYP) 1A2, 2C9, 2D6, or 3A4 substrates. In a dedicated study, relugolix did not prolong QTc at single doses of 60 or 360 mg.

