5.4. Directions for Administration

Relugolix

Relugolix 120-mg tablet strength will be available as immediate-release film-coated tablets. These tablets will be presented in 45-tablet bottle packaging and dispensed to patients every 4 weeks at scheduled study visits.

All protocol-specific criteria for administration of study drug must be met and documented prior to study drug administration. Study drug will be dispensed by study personnel only to eligible patients who are under the supervision of the investigator or identified subinvestigator(s). If a blood draw or any study procedure coincides with a meal, the study procedure will take precedence, followed by the blood draw, and then the meal.

At the Baseline Day 1 visit, the site will administer a single loading dose of oral relugolix 360 mg (3 tablets).

Patients randomized to relugolix will be instructed to take one tablet on an empty stomach at least 1 hour before breakfast once daily. If the dose is missed in the morning for any reason, the study treatment may be taken later in the day, under fasting conditions, at least 1 hour before or 2 hours after eating a meal. The study treatment should be taken as close as possible to the same time of morning each day.

Patients may consume water ad libitum. Patients should swallow the study medication whole and not chew it or manipulate it in any way before swallowing.

Patients will hold their study treatment on clinic visit days and record the time of their previous dose (ie, the time that they took their dose on the day before the clinic visit); they will be instructed to take their study treatment in the clinic after PK and pharmacodynamic samples are collected.

Leuprolide Acetate

Leuprolide acetate 3-M depot injection, 22.5 mg (or 11.25 in Japan, Taiwan, and China), will be administered every 12 weeks. Leuprolide acetate 3-M depot will be administered on Day 1 at the clinic, then at 12-week intervals (see Schedule of Activities, Section 1.1) and investigators should follow product instructions provided by the manufacturer. An antiandrogen may be administered for the first 4 weeks or longer if indicated, as determined by the investigator, and/or as indicated by disease status (eg, in patients with extensive localized symptomatic disease or with metastatic disease).

Possible antiandrogen options include, but are not limited to, bicalutamide, flutamide, and nilutamide.

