 - Weight will be collected only on Weeks 13 and 25;
- 12-lead ECG (Weeks 5, 13, and 25 only);
- ECOG performance assessment (Week 25 only);
- Symptom-based physical examination (except Week 25);
- Complete physical exam and visual acuity assessment (Week 25 only);
- Laboratory collection (see Section 1.1)
 - Blood samples for PK analysis will be collected for all patients assigned to the relugolix treatment arm. Samples will be collected predose, approximately 24 hours after the previous dose. Patients may be dosed in the clinic at these visits, provided the dose can be administered at least 2 hours after food; food should be withheld for 1 hour after dosing.
- Concomitant medications and adverse events; and
- Study drug management:
 - For patients randomized to relugolix,
 - Perform study drug accountability;
 - Dispense study drug. Patients may be dosed in the clinic, provided the dose can be administered at least 2 hours after food; food should be withheld for 1 hour after dosing;
 - Remind patients on importance of medication compliance.
 - For patients randomized to leuprolide acetate,
 - Site will administer leuprolide acetate in clinic every 12 weeks (Weeks 13, 25, and 37).

Week 49 or (Early Termination of Study Drug) (Visit Window ± 7 Days)

- For patients receiving relugolix, a member of the site team will call the patient 7 days before the Week 49 visit to remind the patient of the need for compliance with their study medication;
- Patient-reported outcome questionnaires
 - Patients will complete the questionnaires on the tablet provided before other study procedures, such as blood draws and physical examinations, are performed;
- Vital signs, weight;
- 12-lead ECG;
- ECOG performance assessment;
- Complete physical exam and visual acuity assessment;

- Laboratory collection (see Section 1.1);
 - Blood samples for PK analysis will be collected for all patients assigned to the relugolix treatment arm. Samples will be collected predose, approximately 24 hours after the previous dose.
- Concomitant medications and adverse events; and
- Study drug management:
 - For patients randomized to relugolix,
 - Perform study drug accountability.

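### Section 6.6.1.2 sets the food rule for clinic doses at PK visits as 2 hours before food, where the Schedule footnotes and Section 6.3 require 2 hours after food

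*Protocol*

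**What the plan says.** Section 6.6.1.2, under its relugolix sub-heading, allows patients to take the dose in the clinic at PK visits and states that it is "administered on an empty stomach or at least 2 hours before food, and food will be withheld for 1 hour after dosing".

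The other places that govern these clinic doses put the fast before the dose:

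- Section 1.1, footnote m (PK samples in all relugolix patients): clinic dosing is allowed "provided the dose can be administered at least 2 hours after food; food should be withheld for 1 hour after dosing".
- Section 1.1, footnote n (China and Japan PK subset, Day 1 and Week 2 profile doses): "The dose will be administered at least 2 hours after food; food should be withheld for 1 hour after dosing". The same footnote sets the profile sampling: "additional samples collected predose, and 0.5, 1, 2, 4, 6, 8, 12, and 24 hours post-dose on Day 1 and Week 2 visits".
- Section 6.3 (Weeks 5 to 45): "Patients may be dosed in the clinic, provided the dose can be administered at least 2 hours after food", again followed by a 1-hour hold.

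The general dosing rule has two limbs. Section 2.2.4.1: "Relugolix is to be administered in the fasted state (at least 1 hour before or 2 hours after a meal". Section 5.4, for a dose missed in the morning: "under fasting conditions, at least 1 hour before or 2 hours after eating a meal".

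**The concern.** One section of the protocol has *before* where the sections governing the same clinic doses have *after*. This is a live instruction to sites in the procedures section, so it cannot be passed over as background text or left to the statistical analysis plan.

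What is at stake is the fasted condition for the post-dose profiles in the China and Japan subset. Cmax, AUC over the dosing interval and tmax from that subset are listed as secondary endpoints. They are measured from 0.5 to 24 hours after the dose, so the conditions of that day's dose bear on them directly. A man dosed soon after a meal would be expected to show lower exposure than a fasted man.

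**Working it through.** The check is a comparison of texts. The plan states no figure on this point that needs reproducing.

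**Step 1. Set the rules side by side.**

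| Place | Food-free time before the dose | Food-free time after the dose |
|---|---|---|
| 1.1, footnote m | at least 2 h | 1 h |
| 1.1, footnote n | at least 2 h | 1 h |
| 6.3, Weeks 5 to 45 | at least 2 h | 1 h |
| 6.6.1.2, first alternative (empty stomach) | fasted, no time given | 1 h |
| 6.6.1.2, second alternative (2 h before food) | none stated | at least 2 h, which also covers the 1 h hold |

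**Step 2. Find the difference.** The two alternatives in 6.6.1.2 are joined by *or*, so meeting either is enough. Take a man dosed soon after breakfast who then eats nothing for 2 hours. He satisfies the second alternative and the 1-hour hold, but fails footnotes m and n and Section 6.3.

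**Step 3. Test whether it is a slip.** Changing *before* to *after* gives 2 h before the dose and 1 h after it, which is the rule in footnotes m and n and Section 6.3. The protocol file also contains the preceding protocol version. Its Section 6.6.1.2 has the same phrase, while its footnote m already says 2 hours after food. So the wording was carried forward. It is neither a deliberate new rule nor an artefact of text extraction.

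**Step 4. Find where it could matter.**

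- *Routine visits.* PK and testosterone samples are drawn before that visit's dose (Sections 1.1 and 6.6.1.1), so the dose cannot change them.
- *Profile visits.* Samples follow the dose on Day 1 and at Week 2. Footnote q confines the second of these to the subset: "Week 2 visit will only occur for patients who are part of the Japan or China subset for PK analysis". Section 6.6.1.2 plans about 20 such patients from Japan, plus patients from China if enrolled.
- *Safeguard.* The profile sampling times are in footnote n and not in 6.6.1.2. Footnote n carries the correct food rule.

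**Step 5. Size of the effect, if it occurred.** Section 2.2.4.1 gives average reductions of 18.8% in AUC and 21.4% in Cmax when the 120 mg formulation is taken with a high-fat, high-calorie breakfast. It summarises the loss of absorption as about 20%. These figures describe a fed dose. They do not predict a shift in this trial's results.

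**The case against.** The strongest reply is that the intent is clear elsewhere and sites will follow it. Footnotes m and n and Section 6.3 give the correct rule, and Section 5.4 tells patients to take the tablet fasted. The sentence in 6.6.1.2 also sits with wording about optional clinic dosing, which suits routine trough visits better than the profile doses. The subset paragraph in that section has no food rule of its own and refers to Section 1.1. All of this stands, and it makes the risk very small. It does not make the sentence right: a site that reads both places meets two different rules.

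Three stronger readings are tempting, but the documents do not support them.

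- *That the sentence contradicts itself.* A reader might infer that 2 hours before food clashes with a 1-hour hold. A dose that meets the first condition automatically meets the second, so the hold is redundant on that limb. On the empty-stomach limb it applies normally.
- *That 6.6.1.2 is looser than Sections 2.2.4.1 and 5.4.* Both of those also carry a limb of at least 1 hour before a meal, and on that limb the 2 hours in 6.6.1.2 is the longer time. If their limb is read together with their fasting wording, the limb in 6.6.1.2 can be read together with its own reference to an empty stomach. The clear contradiction is with footnotes m and n and Section 6.3 only.
- *That the subset's PK results would be biased by a calculable amount.* The number of men who might be dosed fed is unknown. The reported food effect is for 120 mg with a heavy breakfast, whereas the Day 1 dose is 360 mg. At Week 2, drug remaining from earlier doses would dilute the effect of one fed dose by an amount that depends on an assumed PK model.

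**Conclusion.** The point holds as a minor error, wrong as written: 6.6.1.2 contradicts the food rule that footnotes m and n and Section 6.3 set for the same clinic doses. Taken literally, its second alternative drops the fast before the dose.

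It matters only if a site relies on 6.6.1.2 in place of footnote n for a profile dose in the China and Japan subset. For a man dosed that way, the protocol's own average food effect, about 19% on AUC and 21% on Cmax, indicates the order of the loss. This assumes that the effect carries over from the meal and dose studied, and no shift in the group means is claimed. The primary endpoint, the type I error rate and the power are unaffected.

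**What to change.** In Section 6.6.1.2, replace the alternative of an empty stomach or 2 hours before food with *on an empty stomach, at least 2 hours after food*. Keep the 1-hour hold after dosing. The section then agrees with footnotes m and n and with Section 6.3.

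The cost is one phrase, in the next amendment or a clarification letter to sites. Sampling, data collection and analysis do not change.

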6.6.1.3. Pharmacogenomics Sample Collection

Whole Blood Sample for Germline Deoxyribonucleic Acid

Pharmacogenomic analysis may be conducted to examine the contribution of genetic variance on drug response, for example, its efficacy and safety. Participation of study patients in pharmacogenomic sample collection is optional. A pharmacogenomics sample will be collected from patients at all participating study centers, with individual patient consent and per local ethics and regulatory standards. The sample will be retained for germline deoxyribonucleic acid (DNA) analysis of potential genetic determinants of drug safety, drug efficacy or disease response, and drug metabolism.

Every patient must sign informed consent/be consented in order to participate in the sampling of whole blood for DNA analysis. This research may be used to develop a better understanding of the safety and efficacy of relugolix and other study drugs, to increase understanding of the disease/condition being studied, and for improving the efficiency, design and study methods of future research studies.

Two venous whole blood sample (4 mL per sample) for the analysis of germline DNA will be collected at Day 1 from all patients who have provided informed consent. The DNA samples are expected to be collected at the Day 1 visit, but if necessary, may be collected at any visit after randomization. If necessary and feasible, a second aliquot of blood may be taken if isolation of DNA from the first sample was not successful or possible. Germline DNA analysis may be conducted to investigate the contribution of genetic variance on drug response, for example, its efficacy and safety. As pharmacogenomics is an evolving science, currently many genes and their function are not yet fully understood. Future data may suggest a role of some of these genes in drug response or diseases, which may lead to additional hypothesis-generating exploratory research on stored samples.

Individual blood samples for germline DNA analysis, including the result of any analyses and corresponding information will be identified only by a code in a computer database.

The whole blood samples for DNA analysis will be stored securely at the sponsor's location or its designated central laboratory vendor until 10 years after completion of this study (HERO, MVT-601-3201) and/or until the drug development of relugolix is no longer actively pursued by Myovant or its collaborators. The storage period for these samples may be adjusted by country in accordance with local regulatory and/or legal requirements for the storage of research samples.

Such changes will be reflected in the Institutional Review Board (IRB)/Independent Ethics Committee (IEC) country-specific informed consent form. After that time, the samples will be properly destroyed by the central laboratory or designee following approval by the sponsor. The investigator will keep records linking the patient identity with the samples for the time required by applicable law. Patients who consent and provide a pharmacogenomic sample for DNA analysis can withdraw their consent and request disposal of a stored sample at any time.

Directions for sample collection and handling can be found in the investigator site file.

6.6.1.4. Quality of Life

European Quality of Life 5-Dimension 5-Level Assessment

The EuroQol EQ-5D-5L comprises 5 scales and an overall assessment of health status on a visual analogue scale ([Appendix 2](#)). The 5 scales include: mobility, self-care, usual activities, pain and discomfort, and anxiety and depression. The original version, the EQ-5D-3L, includes 3 response options for each scale. However, a new 5-level response-option version, the EQ-5D-5L, has been developed with the following response options: no problems, slight problems, moderate problems, severe problems, and unable to/extreme problems. It is believed that the EQ-5D-5L is superior to the EQ-5D-3L in terms of feasibility, ceiling effects, discriminatory power, and convergent validity. The EQ-5D-5L index values will be calculated from the EQ-5D-5L descriptive system scores based on the Crosswalk value sets [[EuroQol Group, 1990](#); [Brooks, 1996](#); [Herdman, 2011](#); [Janssen, 2013](#)].

European Organisation for Research and Treatment of Cancer Assessments

The EORTC-QLQ-C30 [[Fayers, 2001](#); [Fayers, 2002](#)] ([Appendix 3](#)) and the 25-item prostate cancer module EORTC-QLQ-PR25 [[Spry, 2006](#)] ([Appendix 4](#)) will be administered as specified in the Schedule of Activities (see [Section 1.1](#)).

The EORTC QLQ-C30 core measurement will be used to capture distal outcomes, including physical, social functioning, and overall health-related quality of life. The QLQ-C30 core questionnaire incorporates 30 questions comprising 9 multi-item scales: 5 functional scales (physical, role, cognitive, emotional, and social); 3 symptom scales (fatigue, pain, and nausea and vomiting); and a global health and quality of life scale. Several single-item symptom measures are also included. It is a reliable and valid measure of health-related quality of life in patients with cancer and takes about 11 minutes to administer. The instrument has been validated and used in many countries [[Aaronson, 1993](#)].

The EORTC-QLQ-PR25 is the 25-item Prostate Cancer module (P25) of the EORTC. The EORTC-QLQ-PR25 contains 3 additional symptom scales (urinary, bowel, sexual) and 5 treatment-related items.

